16.0 Statistical Considerations and Methodology

16.1 Overview

This is a single-arm phase II study designed to assess the efficacy of binimetinib and encorafenib in patients with advanced pancreatic cancer and somatic $BRAF^{V600E}$ mutation. Overall response rate (ORR) will be used as the primary endpoint. Based on historical data and clinical experience, an ORR of 10% or less would be of no interest (null hypothesis), and an ORR of 30% or more would be of interest (alternative hypothesis). In addition to ORR, progression-free survival (PFS), overall survival (OS), and adverse event rates will be of specific interest. Analysis of acquired BRAF alterations will be performed as correlative research.

Investigation of the "Know Your Tumor" database shows that this subgroup of BRAF

mutations has an approximate prevalence of 15-20% in KRAS wild type pancreatic cancers. Other studies have found that approximately 2% of pancreatic cancers have activating alterations in BRAF.

To pre-register for this study, patients must have documentation indicating a $BRAF^{V600E}$ mutation. Successful registration to this trial requires that this document be centrally reviewed to confirm the existence of the $BRAF^{V600E}$ mutation. Therefore, we do not expect the number of patients pre-registered to the trial to be notably larger than the number of patients who eventually register to the trial.

16.2 Statistical Design

A Simon two-stage optimal design with relaxed futility stopping will be used (Ivanova, *et al*, 2016). The largest success proportion where the proposed treatment regimen would be considered ineffective is 10%, and the smallest success proportion that would warrant subsequent studies with the proposed regimen in this patient population is 30%. Rates of maintaining stable disease throughout the first 24 weeks on treatment are expected to be between 30% and 60%. The following two-stage design uses 10 or 26 evaluable patients to test the null hypothesis that the true success proportion in this given patient population is at most 10%.

16.21 Primary Endpoint

The primary endpoint in this trial is objective response rate (ORR) at 24 weeks post-registration. An objective response is defined as a complete or partial response with a confirmation scan not less than 4 weeks after the initial scan. Disease status will be assessed using RECIST v. 1.1 criteria. Evaluable patients are defined as those who are eligible, consented, and received any protocol treatment.

16.211 STAGE 1:

Enter 10 evaluable patients into the study. If three or fewer patients experience an objective response or maintain stable disease within the predefined time period, we will consider this treatment ineffective in this patient population, and terminate the study. Otherwise, if four or more patients experience an objective response or maintain stable disease, we will proceed to Stage 2.

16.212 STAGE 2:

Enter an additional 16 patients into the study. If five or fewer patients among the 26 total evaluable patients accrued experience an objective response within the predefined time period, we will consider this treatment ineffective in this patient population. If 6 or more patients out of the 26 total evaluable patients accrued experience an objective response, we may recommend further testing of this regimen in subsequent studies.

16.213 NOTE:

Accrual will not be suspended between stages to allow the first 10 patients to become evaluable, unless undue toxicity is observed.

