16.24 Accrual Time and Study Duration

The anticipated accrual rate is 1-2 patients per month. Therefore, the accrual period for the first stage of this study is expected to be approximately 10 months. If patients are accrued to the second stage, the total accrual period is expected to be approximately 26 months. Should the study continue to full accrual, the primary analysis can begin approximately 32 months after the trial begins; as soon as the last patient has either experienced a confirmed objective response, or been observed for 24 weeks.

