16.4 Safety Monitoring

16.41 Adverse Event Stopping Rule(s)

The stopping rules specified below are based on the knowledge available at study development. We note that the Adverse Event Stopping Rule may be adjusted in the event of either (1) the study re-opening to accrual or (2) at any time during the conduct of the trial and in consideration of newly acquired information regarding the adverse event profile of the treatment(s) under investigation. The study team may choose to suspend accrual because of unexpected adverse event profiles that have not crossed the specified rule below.

Accrual will be temporarily suspended to this study if at any time, we observe events considered to be at least possibly related to study treatment (i.e., an adverse event with attribute specified as "possible", "probable", or "definite") that satisfy the following:

If at any time, 3 of the initial 10 treated patients or 30% or more of all patients (when accrual is greater than 10 patients) have experienced a non-hematologic grade 4 or 5 adverse event.

We note that we will review Grade 4 and 5 adverse events deemed "unrelated" or "unlikely to be related", to monitor the emergence of a previously unrecognized treatment-related adverse event.

- 16.5 Data Monitoring and Reporting
 - 16.51 DSMB Reporting

The study chair(s) and the study statistician will review the study at least twice

per year to identify accrual, adverse event, and any endpoint problems that might be developing. The Mayo Clinic Cancer Center (MCCC) Data Safety Monitoring Board (DSMB) is responsible for reviewing accrual and safety data for this trial at least twice per year, based on reports provided by the MCCC Statistical Office.

Additionally, during the first Simon Stage, if and as soon as two patients have experienced a confirmed partial or complete response to therapy, then the study chair(s) and the study statistician will review the study to determine if the study can be opened for full accrual.

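### Stage 1 can end the trial as ineffective with 2 or 3 responses in 10 patients, at small cost in the planned range; separately, 16.22 and 16.23 give different power for the same design

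*Combined protocol and SAP*

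**What the plan says.** - Section 16.2: "A Simon two-stage optimal design with relaxed futility stopping will be used". The response rates are 10% (null) and 30% (alternative), and 24-week SD is expected to lie between 30% and 60%.
- Section 16.211, first 10 evaluable patients: "If three or fewer patients experience an objective response or maintain stable disease within the predefined time period, we will consider this treatment ineffective". With four or more, Stage 2 opens.
- Section 16.212: "If 6 or more patients out of the 26 total evaluable patients accrued experience an objective response, we may recommend further testing". SD plays no part here.
- Section 16.213: "Accrual will not be suspended between stages to allow the first 10 patients to become evaluable, unless undue toxicity is observed".
- Section 16.51: during the first stage, "if and as soon as two patients have experienced a confirmed partial or complete response to therapy", the study chairs and statistician "will review the study to determine if the study can be opened for full accrual". Section 16.24 uses similar words for completing both stages: "Should the study continue to full accrual".
- Section 16.22 assumes SD uniform on (0.3, 0.6) under the null hypothesis and states alpha 0.0397 and power 80.4%.
- Section 16.23 tabulates 0.04, 0.18, 0.42, 0.66 and 0.84 for response rates 0.10, 0.15, 0.20, 0.25 and 0.30, without naming an SD rate.

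**The concern.** The interim rule and the final rule count different things. Three Stage 1 outcomes, written as (responses, SD), stop the trial despite at least two responses: (2,0), (2,1) and (3,0). If the true response rate is 30%, a trial with 2 responses in 10 has a 75% chance of reaching 6 of 26, and one with 3 has a 90% chance. Meanwhile 16.51 treats two confirmed responses as grounds for a review of full accrual, but neither section mentions the other. At stake are some power against the plan's own 30% target and a clear instruction to the team when these outcomes occur.

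The operating characteristics also depend on the SD rate, because SD decides who passes Stage 1. A reader therefore needs to know which SD rate lies behind each stated figure, and 16.22 and 16.23 disagree at a response rate of 30%.

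**Working it through.** **Inputs.** Response rate p = 0.10 or 0.30 (16.1, 16.2); stage sizes 10 and 16, total 26 (16.2, 16.21); SD rate q from 0.30 to 0.60 (16.2, 16.22); interim and final rules from 16.211 and 16.212.

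**Formula.** With R responses and S patients holding SD among 10,

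P(R,S) = 10! / [R! S! (10−R−S)!] × p^R × q^S × (1−p−q)^(10−R−S).

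The probability of a positive trial is the sum, over outcomes that continue, of P(R,S) × P(Bin(16, p) ≥ 6−R).

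**Step 1: reproduce the stated figures under 16.211 as written.**

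- p = 0.10, q = 0.60: alpha 0.0397, as stated.
- p = 0.30, q = 0.30: power 80.35%, against 80.4% stated.
- Averaged over q uniform on (0.3, 0.6): alpha 0.038, power 83.1%.

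The two figures in 16.22 are thus the worst cases at opposite ends of the SD range, not averages over the distribution named there.

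**Step 2: compare with the 16.23 row** (current rule).

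| Response rate | 0.10 | 0.15 | 0.20 | 0.25 | 0.30 |
|---|---|---|---|---|---|
| 16.23 as printed | 0.04 | 0.18 | 0.42 | 0.66 | 0.84 |
| SD 0.30 | 0.03 | 0.16 | 0.38 | 0.62 | 0.80 |
| SD 0.45 | 0.04 | 0.18 | 0.42 | 0.66 | 0.84 |
| SD 0.60 | 0.04 | 0.18 | 0.42 | 0.66 | 0.84 |

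The printed row fits SD 0.45 to 0.60; the power in 16.22 fits SD 0.30.

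**Step 3: size of the disputed outcomes.** At p = 0.30, q = 0.30, their probabilities are 0.0027 for (2,0), 0.0159 for (2,1) and 0.0053 for (3,0), in total 0.0239. All Stage 1 stops together are P(Bin(10, 0.60) ≤ 3) = 0.0548. The chance of final success is P(Bin(16, 0.3) ≥ 4) = 0.754 after 2 responses and P(Bin(16, 0.3) ≥ 3) = 0.901 after 3. The power lost is

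(0.0027 + 0.0159) × 0.754 + 0.0053 × 0.901 ≈ 0.019, or 1.9 points.

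**Step 4: an exemption for two or more responses.** Stop only if R+S ≤ 3 and R < 2.

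| SD rate | Power at 30%, as written | Power at 30%, with exemption | Continuation at 10%, as written | Continuation at 10%, with exemption |
|---|---|---|---|---|
| average over (0.3, 0.6) | 83.1% | 83.4% | 86.5% | 87.7% |
| 0.30 | 80.4% | 82.2% | 61.8% | 65.9% |
| 0.25 | 77.2% | 81.1% | 48.6% | 55.1% |
| 0.20 | 72.5% | 79.7% | 35.0% | 44.6% |

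With the exemption, alpha is 0.0367 at SD 0.30 and 0.0398 at SD 0.60. It cannot exceed P(Bin(26, 0.1) ≥ 6) = 0.0399, the value with no interim stop.

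**Step 5: compare with a response-only interim rule.** Continuing only with 2 or more responses of 10, with 26 patients and 6 of 26 unchanged, stops 14.9% of trials at p = 0.30 and has power 76.1%. The written rule at SD 0.30 stops 5.5% and has power 80.35%. It keeps the higher power down to an SD rate of about 23.6%.

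**The case against.** The best defence is that the sponsor chose this trade-off knowingly. The stated alpha and power come from 16.211 as written, so the cost already lies inside the 80.4%, and 80.4% is the worst case over the planned range. Two responses in 10 is only modest evidence: it or better occurs with probability 0.264 at a true rate of 10%. All of this stands, and it makes the rule change optional.

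Four stronger readings are tempting, and the documents do not support them.

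- *The rule is not relaxed, because it stops trials that a response-only rule would continue.* That is true of three outcomes only. In aggregate the written rule stops far fewer promising trials (5.5% against 14.9% at SD 0.30).
- *SD at a 30% response rate is really 10% to 40%.* This needs all 20 extra points of response to come from patients who would otherwise hold SD, the most adverse assumption. Section 16.2 gives 30% to 60% without limiting it to the null, although 16.22 ties it to the null hypothesis.
- *The 17-patient series in 1.15 shows SD below 30%.* The series mixes BRAF classes and regimens, its figure legend allows for unevaluable patients, and both V600E cases described were responders. It cannot supply a 24-week SD rate for V600E patients on this combination.
- *Section 16.51 contradicts 16.211.* It sets a review, not a competing stopping rule, and full accrual can simply mean completing both stages. The mismatch is the word opened, since 16.213 does not close accrual between stages unless there is undue toxicity.

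**Conclusion.** Two conclusions of different weight.

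First, stated figures need correcting. For one design and one response rate, 16.22 and 16.23 give 80.4% and 0.84. They rest on different, unnamed SD rates, and neither 16.22 figure is the average over the uniform distribution cited for it (alpha 0.038, power 83.1%).

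Second, 16.211 can call the regimen ineffective with 2 or 3 confirmed responses in 10. Within the planned SD range this costs 0.3 power points on average and 1.9 at most, and type I error is not at risk. The cost becomes material only if SD falls below 30% (3.9 points at 25%, 7.3 at 20%). The documents neither give a source for that floor nor show that SD will be lower. The change is a cheap, optional improvement.

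These figures treat SD as an absolute rate, exclusive of response, and assume both interim and final rules are followed exactly.

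**What to change.** 1. **Correct 16.22 and 16.23.** Name the SD rate behind each figure, for both hypotheses. If 16.211 stays unchanged, print the SD 0.30 and SD 0.60 rows from Step 2, and describe 0.0397 and 80.4% as worst cases at SD 0.60 and SD 0.30. This costs only a revised table and sentence.
2. **Optional improvement to 16.211.** Terminate only if response plus SD is 3 or fewer and fewer than two patients have a confirmed response; otherwise proceed to Stage 2. Keep 26 patients and 6 of 26. The SD 0.30 row becomes 0.04, 0.17, 0.40, 0.64 and 0.82, with alpha at most 0.0398 over SD 0.30 to 0.60. The price is more continuation of an ineffective regimen: 61.8% to 65.9% at SD 0.30, and 35.0% to 44.6% at SD 0.20. Uninterrupted accrual limits that price. Twenty-four weeks is about 5.5 months, so at 1 to 2 patients per month roughly 10 + 5.5 ≈ 16 to 10 + 11 = 21 patients are already entered when the tenth reaches 24 weeks.
3. **Clarification only.** Cross-refer 16.51 to 16.211, state which governs, and replace the phrase about opening for full accrual with wording that agrees with 16.213, such as continuing to full accrual.

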16.22 Power and Sample Size

This two-stage study design outlined in 16.21 assumes the number of successes is binomially distributed, the null success proportion is 0.1, and the alternative success proportion is 0.3. Additionally, we assume the rate of stable disease has a uniform distribution U(0.3, 0.6) under the null hypothesis. Given these, the exact type 1 error rate (alpha) is 0.0397, and the exact power is 80.4% when the true response rate is 30%.

A minimum of 10 and maximum of 26 evaluable patients are required under the stated assumptions, unless undue toxicity is observed. We anticipate accruing an additional 3 patients to account for ineligibility, cancellation, major treatment violation, or other reasons. Maximum projected accrual is therefore 29 patients. All sample size calculations were computed using PASS 15 software.

16.23 Operating Characteristics

The probability of declaring that this regimen warrants further studies (i.e. statistical power) under various success proportions can be tabulated as a function of the true success proportion as shown in the following table.

If the true success proportion is:	0.10	0.15	0.20	0.25	0.30
then the probability of declaring that the regimen warrants further studies is:	0.04	0.18	0.42	0.66	0.84

16.24 Accrual Time and Study Duration

The anticipated accrual rate is 1-2 patients per month. Therefore, the accrual period for the first stage of this study is expected to be approximately 10 months. If patients are accrued to the second stage, the total accrual period is expected to be approximately 26 months. Should the study continue to full accrual, the primary analysis can begin approximately 32 months after the trial begins; as soon as the last patient has either experienced a confirmed objective response, or been observed for 24 weeks.

16.3 Analysis Plan

16.31 Primary Endpoint Analysis

The analysis for this trial will begin at planned time points (see 16.2) and at the time the patients have become evaluable for the primary endpoint. Such a decision will be made by the statistician and Study Chair, in accord with CCS Standard Operating Procedures, availability of data for secondary and correlative endpoints, and the level of data maturity.

16.311 Definition

The primary endpoint for this study is defined in section 16.21. The final ORR point estimate and corresponding 95% confidence interval will be reported.

16.312 Estimation

The proportion of successes will be estimated by the number of successes divided by the total number of evaluable patients. Confidence intervals for the true success proportion will be calculated according to the approach of Clopper and Pearson.

16.313 Over Accrual

If more than the target number of patients are accrued, the additional patients will not be used to evaluate the stopping rule or used in any decision making process. However, they will be included in final point estimates and confidence intervals as though they were accrued in the final stage.

- 16.32 Secondary Endpoint Analysis
 - 16.321 Progression-Free Survival

Progression-free survival (PFS) is defined as the time from registration to the first of either disease progression or death from any cause, where disease progression is determined based on RECIST 1.1 criteria. PFS will be estimated using the Kaplan-Meier method. The median PFS and corresponding 95% confidence interval will be reported. Patients who do not experience disease progression or death while on protocol will be censored at the last disease assessment date.

16.322 Overall Survival

Overall survival (OS) is defined as the time from registration to death from any cause. Analysis of this endpoint will mirror that of PFS (section 16.321).

16.323 Duration of Response

Duration of response is defined as the duration of time from first documentation of an objective response (defined in 16.21) to the earliest date disease progression is documented or death from any cause. Analysis of this endpoint will mirror that of PFS (Section 16.321).

16.324 Time to Response

Time to response is defined as the duration of time from registration to the first documentation of an objective response (defined in 16.21). Analysis of this endpoint will mirror that of PFS (section 16.321).

16.325 Adverse Event Rate

All patients who have initiated treatment will be considered evaluable for adverse event analyses. The rate of patients experiencing a grade 3+ adverse event will be reported. Further analyses of adverse event rates will be considered exploratory.

- 16.33 Correlative Research
 - 16.331 Additional mutations in BRAF or in other related genes as determined by next-generation sequencing from plasma samples will be used to investigate the mechanisms of resistance, either primary or acquired through real time monitoring of the BRAF mutational profile evolution.
 - 16.322 Changes in tumor biomarker

The absolute change and percentage change from baseline at each assessment of CA19-9 of CEA levels will be investigated.

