1.0 Background

- 1.1 Treatment
 - 1.11 Therapy for Pancreatic Cancer

While the treatments for metastatic pancreatic cancer have improved in the last decade, and modern chemotherapy regimens, including FOLFIRINOX and gemcitabine + nab-paclitaxel have improved survival times, the hard reality is that the vast majority of patients do not respond to standard chemotherapy. Specifically, the objective response rate (ORR) with front line FOLFIRINOX or gemcitabine + nab-paclitaxel are 32% and 23% respectively (Conroy et al, 2011; Von Hoff et al, 2013). In the 2nd line setting, those percentages drop considerably. For patients treated with the only FDA-approved second line therapy regimen, 5-flurouracil + nano-liposomal irinotecan, the ORR is only 17%, and the median progression-free (PFS) and overall survival (OS) was only 4 and 6 months, respectively (Wang-Gillam et al, 2016). Multiple other Phase II trials as 2nd line therapy for patients have yielded ORR of 2.5 to 24%, with a PFS typically of 2 - 4 months, and OS typically of 4 - 6 months (Boeck *et al*, 2008; Boeck et al, 2007; Cantore et al, 2004; Cereda et al, 2016; Cereda et al, 2011; Demols et al, 2006; Kim et al, 2012; Milella et al, 2004; Oettle et al, 2000; Tsavaris et al, 2005; Ulrich-Pur et al, 2003; Xiong et al, 2008; Zaniboni et al, 2012).

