2.0 Goals

2.1 Primary Goal

To determine the efficacy of the combination of binimetinib and encorafenib as $\geq 2nd$ line of treatment for patients with metastatic pancreatic cancer with BRAF^{V600E} mutation.

- 2.11 Primary Endpoint Objective response rate at 24 weeks post-registration, as defined by RECIST 1.1.
- 2.2 Secondary Goals To determine in patients treated with the combination of binimetinib and encorafenib as ≥ 2nd line of treatment for patients with metastatic pancreatic cancer with BRAF^{V600E} mutation:
 - 2.21 The median progression-free survival Endpoint: The median time from study registration to clinical or radiographic disease progression or death, whichever occurs first, as defined by RECIST 1.1.
 - 2.22 The median overall survival Endpoint: The median time from study registration to death.
 - 2.23 Duration of Response Endpoint: The median duration of time from first documentation of an objective response to the earliest date progression is documented.
 - 2.24 Time to Response Endpoint: The median duration of time from study registration to the first documentation of an objective response.
 - 2.25 The safety and tolerability Endpoint: The rate of grade 3+ Adverse Events as defined by NIH CTCAE v5.0.
- 2.3 Correlative Research Goal
 - 2.31 To determine the mechanisms of resistance, either primary or acquired through real time monitoring of the BRAF mutational profile evolution.
 - 2.32 Endpoint: Additional mutations in BRAF or in other related genes as determined by nextgeneration sequencing from plasma samples.

3.0 Patient Eligibility NOTE: Waivers to eligibility criteria are not allowed per ACCRU policy

- 3.1 Pre-registration Inclusion Criteria
 - 3.11 Age ≥ 18 years.
 - 3.12 Histological confirmation of a pancreatic malignancy as confirmed by the local pathology lab

- 3.13 Patients whose disease has progressed on (or who were intolerant of) at least one line of therapy for metastatic disease
- 3.14 Patients whose disease has recurred with metastatic disease ≤12 weeks of completion of neoadjuvant or adjuvant systemic chemotherapy; or patients with locally advanced disease whose disease progressed to metastatic disease on, or ≤12 weeks after completion of systemic chemotherapy would also be eligible
- 3.15 Provide informed written consent ≤ 28 days prior to pre-registration.

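### Median time to response, analysed like PFS with no restriction to responders, will usually not be reached at the target response rate and can be a censoring artefact when it is

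*Combined protocol and SAP*

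**What the plan says.** All references are to the combined protocol and SAP.

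- Section 2.24 gives the endpoint as "The median duration of time from study registration to the first documentation of an objective response". The stem of 2.2 refers to treated patients, and no population is named for this endpoint.
- Section 16.324 repeats the definition, "Time to response is defined as the duration of time from registration to the first documentation of an objective response (defined in 16.21"), and adds "Analysis of this endpoint will mirror that of PFS (section 16.321").
- The method pointed to, in 16.321, is "PFS will be estimated using the Kaplan-Meier method", with a median and 95% confidence interval. Its censoring rule is "Patients who do not experience disease progression or death while on protocol will be censored at the last disease assessment date".
- Section 16.22 assumes that "the null success proportion is 0.1, and the alternative success proportion is 0.3", and says "A minimum of 10 and maximum of 26 evaluable patients are required under the stated assumptions". Section 16.212 requires 6 or more responses among the 26.
- Section 16.2 expects 30% to 60% of patients to keep stable disease through 24 weeks. Section 16.22 attaches the same range to the null hypothesis.

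The plan does not say whether time to response covers all evaluable patients or responders only, and does not treat progression or death without response as a competing event.

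**The concern.** A Kaplan-Meier median exists only if the curve falls to one half. Here the event is response, the clock starts at registration, and the trial counts 6 of 26 (23%) as success and 30% as its target. Fewer than half of the patients are expected ever to have the event whose median is the endpoint.

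The mirrored censoring adds a second difficulty. A patient whose disease progresses without response leaves the risk set at the last assessment, and Kaplan-Meier then treats that patient as having the same chance of a later response as those still on treatment. The curve drifts above the true response proportion. If enough patients leave early, it crosses one half although far fewer than half responded.

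Duration of response carries the same cross-reference to PFS but not the problem, because its clock starts at response.

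At stake is one secondary endpoint. A successful trial would probably report the median as not reached, or report a number that does not describe how quickly responders respond. Two analysts choosing different populations would also report different results from the same data.

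**Working it through.** **The plan's own figures.** The plan gives none for this endpoint. As a check that the design is read correctly (continue if 4 or more of 10 have response or stable disease; success at 6 or more responses of 26), an exact calculation gives type 1 error 0.0397 at a stable-disease rate of 0.6 and power 0.8035 at a rate of 0.3. Section 16.22 states 0.0397 and 80.4%.

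**Step 1. Non-responders kept at risk.** With 26 patients, half means at least 13 responders. With X binomial (26, 0.3), P(X ≥ 13) = 0.0255. The median is not reached in about 97% of trials.

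**Step 2. PFS censoring with the plan's stable-disease rates.** At a 30% response rate, stable disease of 30% to 60% leaves 100 − 30 − 60 = 10% to 100 − 30 − 30 = 40% progressing or dying without response by week 24. Scans fall at about weeks 4, 8, 16 and 24 (section 4.0, note 4, with 28-day cycles). Assumptions: every response is seen by week 24; progression is equally likely at each of the four scans; progressed patients are censored at the progression scan. The plan gives no response timing, so three were tried, with 4,000 simulated trials per cell. Percentage of trials in which the median is reached:

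| Response timing (weeks 4/8/16/24) | SD 30% | SD 45% | SD 60% |
|---|---|---|---|
| Early (50/40/10/0%) | 4.4 | 3.4 | 2.7 |
| Middle (25/40/25/10%) | 9.0 | 4.9 | 2.6 |
| Late (10/30/30/30%) | 15.6 | 7.8 | 3.8 |

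So it is not reached in 84% to 97%. With responses at weeks 8/16/24 (60/30/10%) and progression spread evenly over the 24 weeks, it is not reached in about 93% to 97%.

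**Step 3. How much of a reached median is artefact.** Censoring can only lower the Kaplan-Meier curve for response, so every trial with 13 or more responders reaches the median. The share of reached medians with fewer than half responding is therefore 1 − 0.0255 / P(reached):

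- SD 30%, early, middle, late: 1 − 0.0255/0.0435 = 41%; 1 − 0.0255/0.0903 = 72%; 1 − 0.0255/0.156 = 84%.
- SD 45%: 24%, 47%, 67% by the same formula.
- SD 60%: at most about a third (1 − 0.0255/0.0375 = 32%), with differences close to simulation error. Almost no one is censored early, and the rare median is mostly genuine.

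**Step 4. Faster progression.** Section 1.11 describes other second-line regimens "with a PFS typically of 2 - 4 months, and OS typically of 4 - 6 months". Applying a median PFS of 2 to 4 months to non-responders (an assumption, exponential), the median is reached in 5-9% of trials (early), 10-31% (middle) and 18-53% (late) when censoring is at the progression scan. If censoring is one scan earlier, the range across timings is 12-83%. For the middle timing, medians of 4, 3 and 2 months give 10%, 15% and 31%. Faster progression makes a reached median more likely. The artefact share runs from 1 − 0.0255/0.05 = 49% to 1 − 0.0255/0.527 = 95% with censoring at the progression scan.

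**Step 5. A worked example.** Of 26 patients, 8 respond (2, 3, 2, 1 at weeks 4, 8, 16, 24) and 17 are censored at progression (6, 5, 4, 2). The numbers at risk are 26, 18, 10 and 4.

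- Week 4: 1 − 2/26 = 0.923
- Week 8: × (1 − 3/18) = 0.769
- Week 16: × (1 − 2/10) = 0.615
- Week 24: × (1 − 1/4) = 0.462

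A median of 24 weeks is reported, although 8/26 = 31% responded and the middle responders (4th and 5th of 8) responded at week 8. If instead 2 progress at each scan and 10 stay stable, the same 8 responses give 0.923, 0.797, 0.703 and 0.649, and the median is not reached.

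**Step 6. Responders only.** Expected responders are 26 × 0.3 = 7.8, and P(none) = 0.7^26 = 0.0001. The median can almost always be computed.

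**The case against.** The strongest reply is that the population is open. The stem of 2.2 and the cross-reference to PFS apply equally to duration of response, which can only concern responders, so neither fixes the population here. A non-responder has no date of first response, and a sponsor could fairly say that responders were meant. That stands, and a reader who infers that the objective cannot be answered at all goes too far. But the text does not state the restriction, the clock starts at registration, and the mirrored censoring clause has work to do only if non-responders are included.

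A reader might also infer that the median is not reached because most patients progress first. The documents do not support this. The plan's own rates imply 10% to 40% progressing without response by week 24 at the target, and under the mirrored rule faster progression makes a reached median more frequent. The low response proportion is what keeps the curve above one half.

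It is tempting, too, to say that the curve grossly overstates response. With non-responder PFS of 2 to 4 months and the 60/30/10% timing, its final value averages 42% to 35% against a true 30%. Those inputs come from other second-line regimens, not from the plan's assumptions. Under the plan's stable-disease rates the figure is about 31% to 35% with that timing, and at most 1 − 0.615 = 39% across the three timings in the table.

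Two further points stand. For an all-patient endpoint, not reached is a correct answer when fewer than half respond. And cumulative incidence would not supply a median either, since it also needs 13 of 26.

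**Conclusion.** The point holds as one about a stated method that suits the endpoint poorly and a population left unstated. With all evaluable patients at risk, the median is not reached in about 97% of trials at the 30% target if non-responders stay at risk. Under the mirrored censoring and the plan's stable-disease rates it is not reached in 93-97% with one assumed response timing, and 84-97% across three others. Reached medians beyond the 2.6% with 13 or more responders are artefacts of censoring. They predominate when progression is fast or responses come late, but not at 60% stable disease.

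The result that the median is rarely reached if non-responders stay at risk needs only the 30% target and 26 patients. The other ranges rest on assumed response timing, progression timing and censoring date.

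The endpoint is secondary and descriptive. A reader should not infer that the reported response rate or the decision rule is affected: these use response counts and a Clopper-Pearson interval.

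**What to change.** In 2.24 and 16.324, define time to response among patients with a confirmed objective response, measured from registration to first documentation. Report the median and range, labelled as descriptive and conditional on response. Delete from 16.324 the sentence that makes the analysis mirror PFS.

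If an all-patient summary is wanted, add the cumulative incidence of response, with progression or death without response as the competing event. Report it as a curve or as values at scan times, without expecting a median from it.

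The cost is about one sentence in each of two sections. No new data are needed, and design, sample size and primary analysis stay as they are. The downside is that the figure then describes responders only, which its label must say.
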